## 7.0 Study Intervention/Investigational Agent

1.1 Description: *Describe the study intervention and/or investigational agent (e.g., drug, device) that is being evaluated.*

**Response:** Orthodontic archwire of rectangular shape with dimensions of 0.016 x 0.022" and the following composition TiNbTaZr (GUMMETAL). Its reported properties include: non-linear superelasticity, ductility of 10x that of conventional metals, lack of work-hardening, extremely low modulus of elasticity (40 GPa), high tensile strength (1100 MPa), low friction, high springback without hysteresis and biocompatibility.

7.1 *Drug/Device Handling: If the research involves drugs or device, describe your plans to store, handle, and administer those drugs or devices so that they will be used only on subjects and be used only by authorized investigators.*

- *If the control of the drugs or devices used in this protocol will be accomplished by following an established, approved organizational SOP (e.g., Research Pharmacy SOP for the Control of Investigational Drugs, etc.), please reference that SOP in this section.*

**Response:** N/A

## 8.0 Local Number of Subjects

8.1 *Indicate the total number of subjects that will be enrolled or records that will be reviewed locally.*

**Response:** 16 patients

8.2 *If applicable, indicate how many subjects you expect to screen to reach your target sample (i.e. your screen failure rate).*

**Response:** 60-70 patients

8.3 *Justify the feasibility of recruiting the proposed number of eligible subjects within the anticipated recruitment period. For example, how many potential subjects do you have access to? What percentage of those potential subjects do you need to recruit?*

**Response:** We will be collaborating with the entire patient pool in our orthodontic residency clinic for the first- and second-year residents. Research examiner will instruct residents doing patient screenings and acceptance of patients on criteria necessary to become a subject in the current study. Research examiner will then evaluate all eligible subjects and see if they meet all inclusion criteria and proceed to inform the subjects of their eligibility and purpose of the study. Each resident can screen approximately 20-30 patients in the course of 2-3 months. If we utilize the patient pools of twelve residents, we can approximate 240 patients total of which the study needs only 6.67% of to get 16 subjects.

## 9.0 Inclusion and Exclusion Criteria\*

9.1 *Describe the criteria that define who will be **included** in your final study sample.*

*NOTE: This may be done in bullet point fashion.*

**Response:**

- Adolescents of both gender (12-17Y11M),
- undergoing orthodontics treatment with full fixed appliances,
- good oral hygiene / health,
- with bilateral spaces  $3 \geq$  mm distal to the maxillary permanent canines,
- normal and hypodivergent growth patterns.

9.2 *Describe the criteria that define who will be **excluded** from your final study sample.*

*NOTE: This may be done in bullet point fashion.*

**Response:**

- Systemic diseases or syndromes,
- abnormalities in tooth shape and/or size,
- previous orthodontic treatment,
- medications that can affect the outcome of the study,

- craniofacial anomalies,
- periodontal disease or attachment loss,
- significant root resorption prior to or during the study (more than 1/3rd root length).
- Patients with known allergy to nickel

9.3 *Indicate specifically whether you will include any of the following special populations in your study using the checkboxes below.*

**NOTE: Members of special populations may not be targeted for enrollment in your study unless you indicate this in your inclusion criteria.**

Response:

- Adults unable to consent
- Individuals who are not yet adults (infants, children, teenagers)
- Pregnant women
- Prisoners

9.4 *Indicate whether you will include non-English speaking individuals in your study. Provide justification if you will exclude non-English speaking individuals.*

*In order to meet one of the primary ethical principles of equitable selection of subjects, non-English speaking individuals may **not** be routinely excluded from research as a matter of convenience.*

*In cases where the research is of therapeutic intent or is designed to investigate areas that would necessarily require certain populations who may not speak English, the researcher is required to make efforts to recruit and include non-English speaking individuals. However, there are studies in which it would be reasonable to limit subjects to those who speak English. Some examples include pilot studies, small unfunded studies with validated instruments not available in other languages, studies with numerous questionnaires, and some non-therapeutic studies which offer no direct benefit.*

**Response:** We will not be including Non-English-speaking subjects. All of the treatment is available as Standard of Care and no potential benefits would be inequitably withheld from Non-English-speakers.

## 10.0      Vulnerable Populations\*

*If the research involves special populations that are considered vulnerable, describe the safeguards included to protect their rights and welfare.*

*NOTE: You should refer to the appropriate checklists, referenced below, to ensure you have provided adequate detail regarding safeguards and protections. You do not, however, need to provide these checklists to the IRB.*

*10.1 For research that involves **pregnant women**, safeguards include:*

*NOTE CHECKLIST: Pregnant Women (HRP-412)*

Response:

**N/A:** This research does not involve pregnant women.

*10.2 For research that involves **neonates of uncertain viability or non-viable neonates**, safeguards include:*

*NOTE CHECKLISTS: Non-Viable Neonates (HRP-413), or Neonates of Uncertain Viability (HRP-414)*

Response:

**N/A:** This research does not involve non-viable neonates or neonates of uncertain viability.

*10.3 For research that involves **prisoners**, safeguards include:*

*NOTE CHECKLIST: Prisoners (HRP-415)*

Response:

**N/A:** This research does not involve prisoners.

*10.4 For research that involves **persons who have not attained the legal age for consent to treatments or procedures involved in the research (“children”)**, safeguards include:*

*NOTE CHECKLIST: Children (HRP-416)*

Response:

- Adequate provisions will be made for soliciting the permission of parents or guardians
- Adequate provisions will be made for soliciting the assent of the children
- No greater than minimal risk to children will be present
- Permission is to be obtained from one of the parents

**N/A:** This research does not involve persons who have not attained the legal age for consent to treatments or procedures (“children”).

*10.5 For research that involves **cognitively impaired adults**, safeguards include:*

*NOTE CHECKLIST: Cognitively Impaired Adults (HRP-417)*

Response:

**N/A:** This research does not involve cognitively impaired adults.

**10.6 Consider if other specifically targeted populations such as students, employees of a specific firm, or educationally or economically disadvantaged persons are vulnerable. Provide information regarding their safeguards and protections, including safeguards to eliminate coercion or undue influence.**

Response: We are not specifically targeting a vulnerable group

## 11.0 Eligibility Screening\*

**11.1 Describe screening procedures for determining subjects' eligibility.**  
Screening refers to determining if prospective participants meet inclusion and exclusion criteria.

*Include all relevant screening documents with your submission (e.g. screening protocol, script, questionnaire).*

**Response:** Patients will arrive to the clinic for a standard clinic screening appointment. Patient eligibility will be reviewed in the EMR after the intake appointment. Once the treating resident and supervising faculty have diagnosed and treatment planned the case, the supervising research resident will be notified. The research resident will communicate with the treating resident about the patient's diagnosis and proposed treatment plan prior to the patient's consultation. Eligibility of patients to the research will be decided from the diagnostic data and proposed treatment plan. If the individual has a treatment plan that meets eligibility criteria, they will be considered as eligible subjects.

**N/A:** There is no screening as part of this protocol.

## 12.0 Recruitment Methods

**N/A:** This is a records review only, and subjects will not be recruited. NOTE: If you select this option, please make sure that all records review procedures and inclusion/exclusion screening are adequately described in other sections.

**12.1 Describe when, where, and how potential subjects will be recruited.**

*NOTE: Recruitment refers to how you are identifying potential participants and introducing them to the study. Include specific methods you will use (e.g. searching charts for specific ICD code numbers, Research Participant Groups, posted advertisements, etc.).*

**Response:** they

There will not be any recruitment materials utilized in this research study. Once the patient is deemed eligible per the procedures in 11.1, the supervising researcher will be present during the treating resident's standard clinic consultation with the patient. During the consultation the researcher will introduce

the research study and explain all aspects / what to expect if they were to consent to participate. All consent and study paperwork will be present during the consultation for the patient to review, ask questions and sign if they consent.

**12.2 Describe how you will protect the privacy interests of prospective subjects during the recruitment process.**

*NOTE: Privacy refers to an individual's right to control access to him or herself.*

**Response:** Patients will be invited to participate in the current study in an separate room away from other patients, during their standard clinic consultation visit.

**12.3 Identify any materials that will be used to recruit subjects.**

*NOTE: Examples include scripts for telephone calls, in person announcements / presentations, email invitations.*

 For advertisements, include the final copy of printed advertisements with your submission. When advertisements are taped for broadcast, attach the final audio/video tape. *NOTE: You may submit the wording of the advertisement prior to taping to ensure there will be no IRB-required revisions, provided the IRB also reviews and approves the final version.*

**Response:** N/A

## **13.0 Procedures Involved\***

**13.1 Provide a description of **all research procedures or activities** being performed and when they are performed once a subject is screened and determined to be eligible. Provide as much detail as possible.**

*NOTE: This should serve as a blueprint for your study and include enough detail so that another investigator could pick up your protocol and replicate the research. For studies that have multiple or complex visits or procedures, consider the addition of a schedule of events table in in your response.*

**Response:** Once the subject has been screened and been deemed eligible to participate in the study the following procedures will take place.

Standard of Care:

- Conventional Full Fixed appliances will be bonded to all permanent teeth (either 0.018" or 0.022" MBT prescription brackets), the maxillary canine bracket prescription will be 0.018" MBT (0.018" straight wire brackets MBT; 3M Oral Care, St. Paul, MN, USA)
- Phase of leveling and aligning will proceed through standard archwire progression, until 0.016 x 0.022" sized wire is able to be engaged.

- Sliding mechanics of canine retraction utilizing NiTi Closed Coil Springs to produce 150g of retraction force, utilizing the first molars and premolars as anchoring units.
- Correx Orthodontic Gauge will be utilized to verify 150g of force generation.

Research:

- A split mouth design will be utilized per patient, randomly assigning the upper left and right sides of the maxilla, through a random number generator.
- Split archwire design will utilize a crimpable binding mechanism to allow for joining of the SS and GUMMETAL wires together dividing at the junction of the maxillary central incisors.
- Patient's occlusion will be disclused to prevent interferences prior to retraction mechanics utilizing bite-turbos on the buccal inclines of the palatal cusps of the maxillary first molars.
- Intraoral scan will be taken utilizing an iTero intraoral scanner prior to beginning retracting mechanics on the upper canines (this will be timepoint T0).
  - Appointment date, patient name, age, sex and position of Canine T0 will be collected into the data sheet.
- If there is a need for absolute anchorage, miniscrews will be utilized on a per case basis.
- T1 will begin canine retraction on both side of the maxillary arch.
  - Intraoral scan will be done
  - Data collection will be done: appointment date, patient name, position of Canine T1
- Each activation of the NiTi Closed Coil spring will be performed by the research examiner.
- After four weeks the patient will return for an adjustment visit:
  - Intraoral scan will be done
  - Data collection will be done: appointment date, patient name, position of Canine T2
  - Reactivation of retraction coil will be done
- After another four weeks the patient will return for an adjustment visit:
  - Intraoral scan and data collection will be done
  - This will mark T3 and reactivation of the retraction coil will be done by the research examiner.
- Final four weeks of retraction the patient will return for an adjustment visit:
  - Final intraoral scan, intraoral photographs, radiographs and data collection will be done marking T4 of data collection.
- There will be no more data collection following the T4 data collection point. The patient will continue orthodontic treatment per the treating resident's treatment plan agreed upon during the consultation.

- Data analysis will be performed by the researcher and statistician from the data collected from the patient.
  - Four consecutive digital models will be superimposed using 3-Shape analyzer software. Color-coded superimposition will be performed to verify the accuracy and precision of the superimposition.
  - To evaluate rate of canine retraction, total retraction distance and 3D tooth control, will be measured through the superimposition models
- Canine movement rate (mm/month) and total retraction distance (mm) will be assessed for the patient based on the position of the canine starting at T0 to T4.

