## 2.0 Study Summary

Study Title	A comparison between TiNbTaZr (GUMMETAL) and stainless-steel alloy for space closure with sliding mechanics A pilot randomized clinical trial
Study Design	Pilot randomized clinical trial
Primary Objective	1. Evaluate the total amount of canine retraction (mm) using GUMMETAL and Stainless-steel archwires 2. Evaluate the rate of canine retraction (mm/month) from T 0 -T 4 .
Secondary Objective(s)	3. Assess the 3-Dimensional control of canines during retraction from T 0 -T 4 .
Research Intervention(s)/Investigational Agent(s)	Orthodontic archwires: GUMMETAL vs. Stainless-Steel
IND/IDE #	N/A
Study Population	12-17Y11M male and female patients
Sample Size	16
Study Duration for individual participants	4 months

Study Specific Abbreviations/ Definitions	TiNbTaZr = GUMMETAL SS = Stainless Steel NiTi = Nickel Titanium
--	---

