## 6.0 Study Design\*

6.1 *Describe and explain the study design (e.g. case-control, cross-sectional, ethnographic, experimental, interventional, longitudinal, observational).*

Response: This will be a randomized pilot split-mouth clinical trial of patients with spaces  $\geq$  3mm distal to the maxillary canines in need of closure through sliding mechanics. The sample consists of adolescent patients regardless of Angle's molar malocclusion who are receiving comprehensive full fixed appliance orthodontic treatment. Preformed conjoint archwires half being GUMMETAL and the other half SS, will be utilized. Each patient will have one side of the maxilla randomly allocated into the SS or GUMMETAL treatment group. The study will follow a split-mouth design to reduce the confounding variables from patient to patient on space closure mechanics. The maxillary arch in each subject will be randomized into a SS side or GM side using a random number

generator. Spaces will be measured at; T0 is initial records, T1 is initiation of space closure, T2 will be 4 weeks after the initiation of space closure, T3 is another 4 weeks of space closure evaluation and T4 will be the final evaluation of space closure after 4 weeks from T3, via 3D intraoral scans of maxillary arches. Space measurement and calculations will utilize 3Shape software to measure the distance of canine movement based off the distal surface. Sliding mechanics will be activated through NiTi coil springs from the maxillary canines to the maxillary molars. The force will be standardized to 150 gms and will be measured each visit. The same provider will activate the NiTi coil spring for retraction, along with data collection. Superimposition of scans will be utilized to assess outcome measures.

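### Retraction rate, total distance and 3D control are measured from T0 although retraction starts at T1, so the pilot's absolute mm and mm/month values may be misstated (minor)

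*Combined protocol and SAP*

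**What the plan says.** **Outcome window.** The analysis bullets of Section 13.1 state that "total retraction distance (mm) will be assessed for the patient based on the position of the canine starting at T 0 to T 4"; the same sentence covers the mm/month rate. Section 2.0 lists, as a primary objective, "Evaluate the rate of canine retraction (mm/month) from T"0 to T4, and, as the secondary objective, "Assess the 3-Dimensional control of canines during retraction from T"0 to T4.

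**Timepoints.** Section 6.1: "T0 is initial records, T1 is initiation of space closure, T2 will be 4 weeks after the initiation of space closure". T3 and T4 follow at further four-week steps. Section 13.1 places the T0 scan "prior to beginning retracting mechanics on the upper canines (this will be timepoint T 0") and then says "T 1 will begin canine retraction on both side of the maxillary arch". T1 has its own scan, and "Data collection will be done: appointment date, patient name, position of Canine T 1". Section 14.2 puts initial records at T0, treats T1 as the start of the study, and gives four months as the full duration.

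**Models.** Section 13.2 lists canine position at all five timepoints. Section 13.1 superimposes four successive models and takes rate, distance and 3D control from them, without naming the four.

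**Not given anywhere in the text:** the T0–T1 interval, the time divisor for the rate, and what counts as a month.

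**The concern.** The outcome window opens before the force that defines the intervention is applied. If T0 and T1 are different visits, following Section 13.1 literally puts time without retraction force, movement from other causes, or both, into the two primary outcomes and the secondary one.

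The rule also cannot be carried out as written. A T0-to-T4 displacement needs both the T0 and the T4 model, and four successive models out of five never include both. The analyst must therefore choose a baseline and a divisor, possibly after seeing data.

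At stake are the absolute distances and rates. The protocol's background (Sections 5.1 and its purpose statement) says that no study of this wire in sliding canine retraction has been published. Readers would therefore be likely to use this pilot's mm/month when planning a larger trial.

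**Working it through.** **The plan's own figure.** Section 20.2 gives 16 patients for 80% power at 0.05 and a 0.5 mm difference. It gives no SD, so 16 cannot be reproduced. Solving backwards for a two-sided paired t-test gives an SD of differences of 0.667 mm. Only the power illustration in step 5 uses an SD of about this size.

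**1. Timeline.** T1 to T4 is 3 × 4 = 12 weeks = 84 days, and 84/30.4375 = 2.760 months. Four calendar months is 4 × 30.4375/7 = 17.39 weeks.

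**2. Models.** Four successive scans out of T0, T1, T2, T3, T4 are either T0–T3 (no final scan) or T1–T4 (no T0 baseline).

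**3. Divisor alone.** Suppose the canine does not move before T1 and the gap is g weeks. A T0–T4 divisor multiplies the T1–T4 rate by 12/(12+g). All gaps are assumptions.

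| Divisor | Factor | Error in rate |
|---|---|---|
| g = 0 (same day) | 12/12 = 1.00 | 0% |
| g = 1 week | 12/13 = 0.923 | −8% |
| g = 2 weeks | 12/14 = 0.857 | −14% |
| g = 4 weeks | 12/16 = 0.750 | −25% |
| stated four months | 2.760/4 = 0.690 | −31% |

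Counting T1–T4 as three months gives 2.760/3 = 0.920, or −8% against calendar months. The definition of a month therefore matters even with the right baseline.

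**4. Movement before T1.** Let d be canine movement from T0 to T1 (distal positive, mesial negative) and D the T1–T4 distance. Distance is misstated by d/D, and so is the rate over a T1–T4 divisor. With assumed |d| of 0.1–0.3 mm and assumed D of 2–3 mm, the smallest error is 0.1/3 = 3% and the largest 0.3/2 = 15%. It is positive for distal movement and negative for mesial movement.

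With a T0–T4 divisor the net rate error is (1 + d/D) × 12/(12+g) − 1:

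| | g = 1 week | g = 4 weeks |
|---|---|---|
| distal d | −4.6% to +6.2% | −22.5% to −13.8% |
| mesial d | −10.8% to −21.5% | −27.5% to −36.3% |

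For example, (1 + 0.3/2) × 12/13 − 1 = +6.2% and (1 − 0.3/2) × 12/16 − 1 = −36.3%. The two errors cancel only if d/D = g/12.

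**5. Effect on the wire comparison.**

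- *Constant gap.* One divisor for all patients cancels from the paired t. A simulated set of 16 pairs gave t = 1.936 with divisors of 2.76, 3 and 4. The mm/month difference itself shrinks by the factor in step 3.
- *Varying gap.* Let w = 1/(12+g), with g uniform from 1 to 5 weeks, and r = mean difference/SD. The standardized effect is multiplied by E[w]/√(E[w²](1+r²) − E[w]²r²). This is 0.997 at r = 0.25 and 0.994 at r = 1.0, a loss of under 1%.
- *Unequal movement before T1.* Independent side-to-side differences with SD s raise the SD of differences to √(0.669² + s²). Power falls from about 80% to 76%, 67% and 55% for assumed s of 0.2, 0.4 and 0.6 mm. A mean difference between sides would shift the estimate by that amount.

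**The case against.** The strongest reply is that this barely touches the trial's question. The hypothesis (Section 3.2) and the endpoint (Section 4.0) are comparisons between wires. The gap is common to both sides of a mouth, and the T1 scan, date and position are already collected, so correct values can be recovered. Section 13.1 lists the T0 scan just before retraction, which suggests a short gap, and a same-day T0 and T1 is not excluded. Section 21.2 refers to a monthly rate. If rate is calculated per visit interval, T0–T1 affects only its own interval. The data collection spreadsheet was filed separately and may hold the formula.

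Much of this stands, and it sets the severity. It does not remove the conflict. Sections 2.0 and 13.1 still state T0–T4, separate scans and date entries at T0 and T1 count against a same-day reading, and the choice of four models is unresolved on any reading.

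Three stronger readings are tempting but unsupported:

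- A reader might infer that no baseline is stated. Section 13.1 names T0; the difficulty is that T0 conflicts with the start of retraction and with the four models.
- A reader might infer that visit dates are missing at T3 and T4. At T3 Section 13.1 says only "Intraoral scan and data collection will be done", and T4 is similar. That reads naturally as shorthand for the items listed at T1 and T2, and the patient record is a named source.
- A reader might infer that the comparison between wires is biased. A shared divisor favours neither wire. Only unequal movement before T1 could disturb the comparison, and the documents give no evidence of it.

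**Conclusion.** The point holds as a minor one. The stated T0–T4 window conflicts with retraction starting at T1, cannot be met with the four models, and has no stated divisor.

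The size is unknown because it depends on a gap and a movement that the documents do not give. For the divisor alone it runs from 0% (same day) through −8% (one week) to −25% (four weeks), with −31% if the stated four months is the divisor. A reader might take that last figure as a ceiling. It is not one, because Section 14.2 does not say that the four months include T0–T1, and nothing caps the gap. Nor is understatement certain: distal movement before T1 pushes distance, and rate over a T1–T4 divisor, upwards.

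The paired t is unchanged by a constant gap and nearly so by a varying one. That reassurance covers the divisor only. Unequal movement before T1 would add noise to the comparison or shift it. The main harm is to the absolute values the pilot reports.

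**What to change.** In Sections 2.0 and 13.1:

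- Define total retraction and 3D control as change from the T1 scan to the T4 scan.
- Define rate as that displacement divided by actual elapsed time from T1 to T4, and define the month (for example 30.44 days; another stated convention would also do).
- Name the four superimposed models as T1, T2, T3 and T4.
- Report T0 descriptively.
- If T0 and T1 are meant to be one visit, say so instead, and align the descriptions of T0 in Sections 6.1, 13.1 and 14.2.

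The cost is protocol wording only. The T1 scan, date and canine position are already planned, so no visit or scan is added.
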